## **9 Statistical Considerations**

### **9.1 Sample Size Calculations**

Based on prior studies of diagnostic yield of HD-WLE and NBI in detecting abnormalities in BE we assume that using a cap during BAE will increase the diagnostic yield by 15%. With this assumption in mind and requiring a power of 80% and alpha of 0.05 (two tailed) we would need a total of 170 patients.

### **9.2 Analysis methods**

This study will collect both categorical and quantitative demographic variables and endoscopy procedural details: procedure duration, diagnostic findings, and procedure complications. Pathology results will be recorded and the electronic medical record will be reviewed to extract any relevant clinical information. All complications will be noted. All information will be transferred into a database. The categorical variables will be summarized using frequencies and percents, while the quantitative variables will be summarized using means and standard deviations. Chi square test will be used for categorical variables while student's t test will be used for quantitative variables to test the difference between the study groups. Additionally, multivariable analysis will be used in order to identify factors associated with success increasing diagnostic yield. Continuous variables with a non-normal distribution will be compared using the Wilcoxon rank-sum test. The statistical software program SPSS will be used for analysis. A two sided p value of < 0.05 will be considered significant.

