## **2 Objectives**

### **2.1 Primary Objective**

To compare the diagnostic yield of esophagogastroduodenoscopy (EGD), a test to examine the lining of the esophagus, stomach, and first part of the small intestine, with HD-WLE and NBI with the diagnostic yield of cap-assisted EGD with HD-WLE and NBI. "Diagnostic yield" is defined as the proportion of EGD in which visible BE lesions were identified and confirmed histologically as low grade dysplasia, high grade dysplasia, intramucosal cancer, or invasive adenocarcinoma

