#### **4.4 Randomization**

Consenting and eligible participants will be randomized to one of two arms. Participants in the first arm will undergo EGD with cap first, followed by EGD without cap. Participants in the second arm will undergo EGD without cap first, followed by EGD with cap. All participants will have EGD with and without cap; the randomization affects the order in which the procedures take place. The order of cap placement will be determined by a preprinted randomization sequence kept in an opaque envelope that will be opened after enrollment.

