### 5.2 Intervention

After randomization, the endoscopist will then perform exam with or without cap using HD-WLE and NBI and identify visible lesions. Identified lesions will be recorded on the case report form using a blank clock face divided in four quadrants and with distance from the incisors in cm. The endoscope will then be withdrawn. A second endoscopist will then perform a second EGD with a cap if none was used on initial exam or without a cap if one was used on initial exam. The second endoscopist will be blinded to the results of the initial exam. If there is no physician available to perform second endoscopy then the patient will not be considered for the study. Visible lesions will be recorded in same format as initial exam. Finally, the endoscopist of record will biopsy or perform EMR of all noted lesions, which will be sent for pathological review, the results of which will be captured from the medical record. All procedures will be performed by a gastroenterologist experienced in EET or by a fellow under direct supervision. Patients will be contacted in 48 hours by phone by clinical staff to monitor for AEs

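### Every patient has both a cap and a no-cap exam, but Section 9.2 plans independent-sample tests between undefined groups; on the natural reading the primary test is conservative and can miss a gain below 15 points

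*Combined protocol and SAP*

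**What the plan says.** Section 4.4 sets up a within-patient comparison: "All participants will have EGD with and without cap; the randomization affects the order in which the procedures take place". Section 5.2 has both exams done in the same patient, one after the other: "A second endoscopist will then perform a second EGD with a cap if none was used on initial exam", and the reverse if a cap came first. Section 2.1 defines the primary endpoint, diagnostic yield, as "the proportion of EGD in which visible BE lesions were identified and confirmed histologically" as dysplasia or cancer. The unit is therefore the exam, and each patient supplies two.

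Section 9.2 is the only analysis section. It states "Chi square test will be used for categorical variables while student's t test will be used for quantitative variables", and the purpose is "to test the difference between the study groups". For skewed data, "Continuous variables with a non-normal distribution will be compared using the Wilcoxon rank-sum test". A multivariable analysis is also mentioned, without a unit of analysis. The document names no McNemar test, paired t test, signed-rank test, conditional model, GEE or mixed model. Section 9.1 gives 170 patients for a 15% increase with 80% power and two-sided alpha 0.05, with no baseline yield, discordance or correlation.

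**The concern.** An ordinary chi-square and the rank-sum test assume independent samples, and the Student's t test is not stated to be paired. The groups to be compared can be read in three ways:

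1. **Cap exams against no-cap exams.** This fits Section 2.1 best, but the two samples are the same patients and the pairing is ignored.
2. **The two randomized arms of Section 4.4.** Both arms contain both kinds of exam, so their difference does not estimate the cap effect.
3. **First exams only**, cap-first against no-cap-first. This is valid but discards half the data.

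The primary p-value therefore depends on a choice that could be made after the data are seen. On the natural reading, a real but moderate benefit may be reported as non-significant. The comparison of high grade dysplasia and adenocarcinoma in Section 2.2 has the same problem if it is tested the same way. If the multivariable model uses both exams per patient, nothing says that clustering is handled.

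**Working it through.** **Inputs.** From the documents: 170 patients, two-sided alpha 0.05, power 80%, a 15% increase (Section 9.1), two exams per patient (Sections 4.4 and 5.2). Assumed: complete pairs; the 15% taken as absolute points; no-cap yield of 50% (20% and 30% also run); within-patient correlation ρ from 0 to 0.6; an 85/85 split for the first-exam reading.

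**The plan's figure.** It cannot be reproduced from stated inputs, because no baseline is given. The independent-samples formula, n per group = [1.96√(2p̄q̄) + 0.842√(p₁q₁ + p₂q₂)]²/δ², gives for 50% against 65%: [1.96 × 0.699 + 0.842 × 0.691]²/0.0225 = 169.3, so 170 *per group*. McNemar sizing, [1.96√ψ + 0.842√(ψ − δ²)]²/δ², gives 103, 138 and 169 patients at discordance ψ of 30%, 40% and 49%. At 50% against 65% with ρ = 0, discordance is 50%. So 170 is about what is needed if pairing brings no gain, although that match rests on an assumed baseline.

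**Why pairing matters.** Under the null with common yield p, the difference in yields has variance 2pq(1 − ρ)/n. The chi-square uses 2pq/n. Its true type I error is therefore about 2[1 − Φ(1.96/√(1 − ρ))], which is 1.9%, 0.56% and 0.19% at ρ = 0.3, 0.5 and 0.6.

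**Simulation.** 400,000 trials of 170 pairs per scenario; uncorrected chi-square on 170 against 170 exams, compared with asymptotic McNemar. The smallest detectable gain was found by bisection with 100,000 trials per step.

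| Quantity | Test | ρ = 0.3 | ρ = 0.5 | ρ = 0.6 |
|---|---|---|---|---|
| Type I error, 50% yield | chi-square | 1.7% | 0.5% | 0.2% |
| Power, 50% to 60% | chi-square | 45% | 44% | 43% |
| | McNemar | 60% | 75% | 84% |
| Power, 20% to 30% | chi-square | 59% | 60% | 61% |
| | McNemar | 72% | 86% | 94% |
| Power, 50% to 65% | chi-square | 85% | 89% | 92% |
| | McNemar | 92% | 98% | >99% |
| Smallest gain with 80% power, 50% baseline (points) | chi-square | 14.1 | 13.6 | 13.3 |
| | McNemar | 12.6 | 10.6 | 9.5 |
| Same, 20% baseline (points) | chi-square | 12.6 | 12.1 | 11.8 |
| | McNemar | 11.1 | 9.1 | 8.0 |

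McNemar's type I error stays at about 5%. At ρ = 0 the tests agree (50% to 65%: 81% against 80%). Across all the all-exam scenarios, chi-square power for 15 points ran from 81% to 97%.

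**One possible data set.** Take 72 patients positive on both exams, 30 on cap only, 13 on no cap only and 55 on neither. Yields are 102/170 = 60% and 85/170 = 50%.
- Correlation: (72×55 − 30×13)/√(102×68×85×85) = 0.50.
- Chi-square: 0.10²/(2 × 0.55 × 0.45/170) = 3.43, p = 0.064.
- McNemar: (30 − 13)²/43 = 6.72, p = 0.0095; exact p = 0.014.

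The same patients lead to opposite conclusions.

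**First exams only (85 against 85), 15-point gain.** Type I error is about 5%. Power is 52% (50% against 65%) and 60% (20% against 35%), and passes 80% only at an extreme baseline such as 7% against 22%.

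**The case against.** The strongest reply concerns size. Section 9.1 powers the trial for a 15% increase, and on all exams the chi-square keeps at least 80% power for 15 points and errs on the safe side. McNemar can also miss smaller gains: it has only 60% power for 50% to 60% at ρ = 0.3, where the smallest detectable gain is 12.6 points against 14.1. The documents give no correlation, and a different, blinded second endoscopist may lower agreement. At ρ = 0.1 the loss is small: type I error about 3.6%, and power 46% against 50% for 10 points. At ρ = −0.2 the chi-square would be anti-conservative (about 7%).

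All of that is correct, and it limits the claim to positive correlation and to gains below the target. Positive correlation is nevertheless expected, because a patient with no dysplastic lesion is negative on both exams. Smaller gains are also not remote: Section 1.2 cites 5–10% for caps in colonoscopy, and 69.4% to 83.3% (13.9 points) for diagnosing Barrett's esophagus.

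Two further replies have some force. The objectives point to cap against no cap, so the order-arm reading is the least likely; even so, the only groups the document defines are those arms. And a Student's t test can be paired, so for that test the plan is silent rather than wrong. The chi-square and rank-sum mismatches remain.

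**Conclusion.** The concern holds, and the point must be fixed before analysis. The stated tests do not match the paired design, and the primary contrast is undefined; neither conclusion depends on any assumed rate. The size of the loss does. For a 10-point gain from 50%, the unpaired test gives up about 15 to 41 percentage points of power as ρ runs from 0.3 to 0.6 (60 − 45 and 84 − 43). It does not produce a false claim of benefit when correlation is positive.

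The statement that power is adequate at 15 points applies to the comparison of all exams, not to first exams only, and it takes the 15% as absolute. Section 9.1 does not say which is meant. If it is relative, 50% becomes 57.5%, and at ρ = 0.3 power is about 24% for chi-square and 38% for McNemar.

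**What to change.** Amend Section 9.2 to say:

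- **Primary contrast:** cap against no cap within patient, using both exams of all patients.
- **Primary test:** McNemar on cap-only against no-cap-only positives, exact if discordant pairs are few, with a paired confidence interval for the difference in yield.
- **High grade dysplasia and adenocarcinoma:** McNemar.
- **Lesions per patient and other quantities measured at both exams:** paired t or Wilcoxon signed-rank. If procedure duration is recorded once per patient, a paired test does not apply to it.
- **Multivariable model:** state the unit of analysis. If both exams are used, account for clustering on patient (GEE or mixed logistic model).
- **Chi-square, unpaired t and rank-sum:** keep these for baseline comparisons between the two order arms.

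A model with exam order and cap-by-factor interactions is an optional supporting analysis. It is most useful if the order arms turn out unequal, since Section 4.4 states no allocation ratio.

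The cost is wording only. No new data, visits or patients are needed, and standard software runs these tests. The change should be made before results are seen.

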## **10 MULTICENTER REGULATORY REQUIREMENTS**

Washington University requires that each participating site sends its informed consent document to be reviewed and approved by the Washington University Regulatory Coordinator (or designee) prior to IRB/IEC submission.

Site activation is defined as when the secondary site has received official written documentation from the coordinating center that the site has been approved to begin enrollment. At a minimum, each participating institution must have the following documents on file at Washington University prior to study activation:

- Documentation of IRB approval of the study in the form of a letter or other official document from the participating institution's IRB. This documentation must show which version of the protocol was approved by the IRB.
- Documentation of IRB approval of an informed consent form. The consent must include a statement that data will be shared with Washington University, including the Quality Assurance and Safety Monitoring Committee (QASMC), the DSMC (if applicable), and the Washington University study team.
- Documentation of FWA, signed FDA Form 1572 (if applicable), and the CVs of all participating investigators.
- Protocol signature page signed and dated by the investigator at each participating site.

The coordinating center Principal Investigator (or designee) is responsible for disseminating to the participating sites all study updates, amendments, reportable adverse events, etc. Protocol/consent modifications and IB updates will be forwarded electronically to the secondary sites within 4 weeks of obtaining Washington University IRB approval. Activated secondary sites are expected to submit protocol/consent/IB modifications to their local IRBs within 4 weeks of receipt unless otherwise noted. Upon the secondary sites obtaining local IRB approval, documentation of such shall be sent to the Washington University study team within 2 weeks of receipt of approval.

Documentation of participating sites' IRB approval of annual continuing reviews, protocol amendments or revisions, all SAE reports, and all protocol violations/deviations/exceptions must be kept on file at Washington University.

The investigator or a designee from each institution must participate in a regular conference call to update and inform regarding the progress of the trial.

